### **6.3.2 Blinding**

Both therapist and subject blinding to intervention condition is not feasible. An effort will be made to keep research assistants conducting assessments blind to intervention condition and the plan for balancing number of cohorts assigned to each intervention condition within each CTP site.

### **6.3.3 Quality Control of Therapies Administered**

Quality control of both interventions will be maintained through 4 procedures. These include: 1) Interventions guided by detailed, written intervention manuals – on which training and ongoing administration will be based; 2) Audiotaping of intervention sessions (audiotapes will be reviewed by the Study Counselor Supervisor and/or the CTP Study Site Coordinator or designee; adherence or deviation from manual will be documented and discussed with the therapist during supervision); 3) Completion of fidelity questionnaires by subjects at each follow up assessment interview – to document

exposure to elements of either intervention condition; and 4) Completion of questionnaires by therapists about content covered and activities conducted – to compare to intervention manual specifications.

It should be noted that the risk of contamination of HE sessions from the therapist's SSB training is also minimized by the lack of time in the HE session to include any activities other than the curriculum provided for this session.

## **7.0 Concomitant Therapy**

### **7.1 General Considerations**

During part or all of subjects' participation in the study, they will be participants in their substance abuse treatment. This may include discussion of HIV risk and/or preventive behavior. Subjects may also be exposed to HIV street outreach, media campaigns, and/or other HIV prevention intervention. It would be both unethical and unfeasible to impede these activities. In order to account for these activities, they will be documented through fidelity measures administered to subjects at each follow up assessment interview.

### **7.2 Therapies Prohibited During The Study**

No concomitant therapies are prohibited during the study. Therapists providing the SSB intervention will be instructed to not bring the techniques unique to it into individual sessions during the trial. Subjects will be asked about such exposures on the fidelity measure.

## **8.0 Measurements, Evaluations and Analytical Methods**

Table 1 presents a schema for key study procedures. Study assessments will be conducted at: 1) screening; 2) baseline; 3) immediate post-intervention follow-up; 4) three-month post-intervention follow-up; and 5) six-month post-intervention follow-up. Table 2, at the end of this section, presents a schedule for assessment. Subjects will be informed and assured that data collected from research assessments will not be shared with treatment staff. Prior research has indicated substance abusers are more likely to self-disclose substance use behaviors when there are no legal or clinical contingencies tied to that self-report.

Biologic measures, including urine screens for illicit substance and breathalyzer screens for alcohol use, will be used to substantiate self report data. The inclusion of objective measurements increase the validity of self report assessments.

At the same time, we maintain that there is persuasive empirical evidence of the improved validity of self-report risk assessment, conferred by the ACASI method. For instance, Metzger et al. (2000) has demonstrated higher levels of reported risk behavior by ACASI than by face-to-face interview assessment. In choosing ACASI, we propose that we are using a state-of-the-art, feasible method of reducing social desirability effects.

A major consideration in planning treatment outcome research involves formulation of an effective plan to ensure follow-up data are obtained. To encourage participation in follow-up, the length of each visit has been kept as short as possible. Participants will be paid in cash or vouchers for completion of follow-up assessments. Reasonable and non-coercive reimbursement sums will be determined on a site-by-site basis. If necessary, on a case-by-case basis, study staff will provide childcare during follow-up assessment, if CTP policy permits. It is anticipated that follow-up rates for subjects while they are still in treatment will be extremely high. Subjects who have left the area will be interviewed by phone. A paper/pencil version of the SERBAS (usually administered via ACASI) will be created so as to be able to collect data on subjects who have left the area or are unable to be interviewed in person. All subjects will complete a locator sheet that identifies stable individuals who are likely to know of the subjects' whereabouts in the future. On the regular, study-wide conference calls, study staff will brainstorm solutions to attendance problems, when they emerge.

### **8.1 Informed Consent**

At both screening and entry into the main intervention trial, study staff will obtain informed consent for study participation. Sample consent forms for obtaining written informed consent are provided in the appendix. Consent procedures are described in section 5.3.

### **8.2 Inclusion/Exclusion Criteria Review**

#### **8.2.1 Screening Assessment**

Screening interviews will consist of three steps: (1) Eligibility on the unprotected penetrative sexual activity and ineligibility on pregnancy intention, will be determined; (2) Basic demographic and HIV risk behavior information, including ineligibility due to age < 18, will be determined; and (3) Ineligibility due to gross mental status impairment or incapacity to give informed consent will be determined, from all women who are eligible on behavioral screening. Participants will be paid in cash or vouchers for completion of the screening assessment. Reasonable and non-coercive reimbursement sums will be determined on a site-by-site basis. The screening assessment will not be audiotaped.

The screening assessments include:

**Demographic Form:** A CTN created form collecting basic descriptive data, including age, gender, ethnicity, years of education, occupation, and drug use history.

**Risk Behavior Survey:** The RBS is part of the CTN common assessment battery. It is a brief interview assessing HIV drug use and sexual risk behavior, chiefly during the prior 30 days. Questions C1 – C3 will be repeated for the prior 3 and 6 months. If the client indicates no unprotected heterosexual vaginal or anal sex in the prior 6 months, she will be ineligible for the study.

**Mini-Mental Status Exam (MMSE):** The MMSE (Folstein, Folstein & McHugh, 1975; Cockrell & Folstein, 1988) will be used to identify potential subjects who are too cognitively impaired to engage in the study. Individuals with scores less than 25 will be excluded from the study. MMSE has the advantage of being: 1) widely used in research

protocols for this purpose, 2) relatively easy to administer and score; 3) relatively short; 4) and extremely inclusionary, in that only the most grossly cognitively impaired individuals will be excluded. This instrument will only be administered at the time of screening.

**Basic Data and Locator Questionnaire:** locator information, including home address and phone number, will be collected and kept confidential in the subject's record. Data collected on the Basic Data and Locator Questionnaire will be used to contact the patient for assessment and follow-up and in emergencies. Patients will be asked to provide locator information including their residential street address and a working telephone number, or an address of a relative if they are homeless, as well as the address and telephone number of a non-drug abusing relative or friend who can reach the client in emergencies.

Subjects excluded from study during the screening assessment will not be informed of the reason for exclusion, so as to not bias screening assessments of other potential subjects with whom they may come in contact. Excluded subjects will be told that several criteria must be met before a subject can be enrolled into study, and that, unfortunately, they did not meet one. We do not disclose to subjects the criterion that was not met, so as to limit other potential subjects from being able to misrepresent themselves if they did not meet similar criteria. The screening instruments will only be administered at time of screening.

### **8.3 Baseline and Follow-Up Assessment Battery**

Participants will be paid in cash or vouchers for completion of the baseline and follow-up assessments. Reasonable and non-coercive reimbursement sums will be determined on a site-by-site basis. All randomized participants will be followed throughout the study in order to maximize follow up rates. If possible, participants should be interviewed in person, including participants who might be incarcerated. The protocol specific assessments (not the Common Assessment Battery or ACASI administered SERBAS) within the Baseline and Follow Up Assessment should be audiotaped. The following instruments will be used at baseline and follow-up:

**8.3.1 Composite International Diagnostic Interview (CIDI):** The substance abuse subsections of the Composite International Diagnostic Interview, Version 2.1 (CIDI-2.1), part of the CTN common assessment battery, will be used to determine whether participants meet DSM-IV criteria for substance abuse or dependence. This is administered at the baseline only.

**8.3.2 Addiction Severity Index-Lite:** The ASI, also included in the CTN common assessment battery, is a standardized, multidimensional, semi-structured, comprehensive clinical interview that provides problem severity profiles and treatment planning information in 6 problem domains commonly affected by substance abuse. These problem domains are: alcohol and substance abuse; medical; psychiatric; legal; family/social; and employment/support. Composite scores for each domain are derived mathematically. A revised version of the 1997 ASI Lite 5th Edition, limited to the items used in the composite scores and some demographic information, will be administered by a research staff member. The full ASI-Lite will be administered at the baseline only.

At the 3-month and 6-month assessment, only the drug and alcohol section will be administered.

**8.3.3 Biologic Measures:** Urine and alcohol screens will be done at the Baseline assessment to substantiate self-report data. The urine drug screen will occur onsite and test for 10 illicit substances. A breathalyzer will be used to screen for blood alcohol concentration (BAC).

**8.3.4 Drug Use and Drug Injection Risk Behavior Assessment:** The RBS drug use and injection practice items will be repeated at the 3 and 6 month follow-up visits.

**8.3.5 Eating Disorder Examination Questionnaire (EDE-Q):** Thirty-eight item self report assessing the frequency of key behavioral features, such as binge eating, self-induced vomiting, and associating eating disorder pathology. The instrument includes four sub-scales: restraint, weight concern, shape concern, and eating concern. Focuses on a 28-day time period and uses 7 point rating scale. The scale has good psychometric properties (Cronbach's alphas ranging from .67 to .90). **(optional assessment)**

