### **8.5 Adverse Event Evaluation**

An adverse event (AE) is defined as any reaction, side effect or untoward event that occurs during the course of the clinical trial. The possibility of abusive partner behavior and/or a marked increase in emotional distress (defined as an increase in depression and/or anxiety symptoms) are the foreseeable adverse effects of participation. Possible triggers for these effects could be: introduction of (male or female) condoms or other methods of protection; introduction of safer sex negotiation; refusal of unprotected sex; or partner knowledge of the woman's participation in a woman's intervention. Subjects are advised to observe any signs of anger in their partners, and any of these problems in themselves, and to discuss this with study staff immediately. Study staff will be trained to provide crisis intervention and referral for clinical emergency situations. In addition, all study assessments contain modules concerning abuse that can alert study staff to evolving risk. The occurrence of AEs will be determined through the use of an AE Worksheet (consisting of one general AE question and a follow up question to gather more information) filled out by the RA at baseline, immediate post treatment, 3 and 6 month follow up assessments. All SAEs will be recorded, respectively, on the AE Case Report Form (CRF) and SAE Form and SAE Summary Report. The procedures for detecting, reporting and monitoring SAEs are described in section 9.0.

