## **9.1 Safety**

### **9.1.1 Definition of Adverse and Serious Adverse Events**

Adverse events will be categorized as serious or non-serious, as related or not related to the study, and as expected or unexpected. An adverse event is defined as any reaction, side effect, or untoward event that occurs during the course of the clinical trial. Stable chronic conditions which do not worsen are not considered AEs. Clinically insignificant events will be excluded from any type of documentation. These may include: colds, flu, cuts, scrapes, coughs, headaches, stomach complaints, general fatigue and mild symptoms or problems associated with medical conditions not related to drug use.

A serious adverse event (SAE) is defined as: any fatal event; any immediately life-threatening event; any permanent or substantially disabling event; any event that requires initial hospitalization or prolongs hospitalization (excluding normal childbirth and pre-planned or elective procedures); any event causing congenital anomaly or birth defect; or any event requiring intervention to prevent any of these problems. Hospital visits that do not result in admittance are not considered SAEs (e.g. emergency room visit that does not result in admittance).

Risks from behavioral intervention trials may be expected to be minimal relative to those from pharmacologic interventions. The possibility of abusive partner behavior and/or a marked increase in emotional distress (defined as an increase in depression and/or anxiety symptoms) are the foreseeable adverse effects of participation.

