### **9.1.2 Assessment, Reporting and Monitoring of Adverse and Serious Adverse Events**

AEs and SAEs will be elicited by research assistants at each assessment (baseline through follow up). The RA will ask the subject whether she has experienced any new problems or a worsening of existing problems since her last assessment using the AE Worksheet. The RA should be focused on gathering data to aid the Study Clinician in determining study relatedness. Assessment of depression must include an assessment of suicidal ideation, as suicidal ideation may require immediate clinical assistance and qualify as an SAE. All clinically significant AEs will be captured on a standardized AE Log, with immediate assessment for whether or not the AE is serious, and whether or not the AE is study-related, in consultation with the site coordinator or Study Clinician (PhD, MD, PI). Study-relatedness will ultimately be determined by the Study Clinician following discussion with the staff member reporting the AE. AEs that are not serious or study related do not require any further paperwork documentation besides the AE Log. AEs and SAEs could also be spontaneously disclosed by the subject during intervention sessions. In this case, the therapist will record and report them, as described here.

Study staff will be trained to provide crisis intervention and referral for clinical emergency situations. Standard CTP procedures for handling crisis situations should be used. The Site Coordinator and/or Study Clinician will be available by beeper (or other similar method), within 24-hours for consultation and crisis intervention for problems.

From baseline informed consent discussion onward, subjects are advised that conversation about HIV or STDs, introduction of (male or female) condoms or other methods of protection, safer sex negotiation, refusal of unprotected sex, or, even their participation in a women's intervention may anger their male partners. This anger may put them at risk for emotional, physical and/or sexual abuse. Subjects are also advised that emotional distress could develop or increase in response to these problems. For this reason, subjects are advised to observe any signs of such anger in their partners, or such problems in themselves, and to discuss them with study staff immediately. In addition, study assessments contain modules concerning abuse, which can alert the study staff to evolving risk.

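### Increased depression or anxiety, a named foreseeable harm, is followed only through adverse-event reports, so it can be reported but not quantified or fairly compared between arms

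*Protocol*

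**What the plan says.** Section 8.5 states that abusive partner behaviour and/or "a marked increase in emotional distress (defined as an increase in depression and/or anxiety symptoms) are the foreseeable adverse effects of participation". Section 9.1.1 repeats the definition.

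The same section names the detection tool, an AE Worksheet "consisting of one general AE question and a follow up question to gather more information", which the research assistant completes at baseline, immediately after treatment, and at 3 and 6 months. Section 9.1.2 adds that the participant is asked about new or worsening problems since her last assessment, that therapists record events disclosed in sessions, and that "Assessment of depression must include an assessment of suicidal ideation".

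On instruments, Section 8.3.2 describes the ASI-Lite: "These problem domains are: alcohol and substance abuse; medical; psychiatric; legal; family/social; and employment/support". It then limits its use: "The full ASI-Lite will be administered at the baseline only", and "At the 3-month and 6-month assessment, only the drug and alcohol section will be administered". Table 2 agrees with this.

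On recording, Section 9.1.2 enters only serious and study-related events into the database; other events go no further than the AE Log. Section 11.7 classifies each participant by the worst severity reported in the intervention phase.

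**The concern.** The harm is defined as a change in symptoms. To say how large the change is, or whether it is larger under SSB than under HE, the same thing has to be measured before and after, and in the same way in both arms. The plan collects a psychiatric score once, before randomisation, and then drops that part of the instrument. Section 9.1.2 also refers to an assessment of depression that Section 8 does not describe and Table 2 does not schedule.

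At stake is whether the trial could show that the more intensive intervention distresses participants. SSB asks women to raise condom use and negotiation with partners, and Section 8.5 lists these as possible triggers. The other foreseeable harm, abuse, has a repeated measure; distress has none.

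**Working it through.** The plan states no figure to reproduce. The check sets the definition of the harm beside the schedule, the recording rule and the analysis rule.

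**1. Schedule.** There are four assessment points from baseline on: baseline, immediate post-intervention, 3 months and 6 months.

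| Source | Baseline | Post | 3 mo | 6 mo | Count |
|---|---|---|---|---|---|
| ASI-Lite psychiatric domain (8.3.2, Table 2) | yes | no | no | no | 1 of 4 |
| Other depression or anxiety scale (Section 8, Table 2) | no | no | no | no | 0 of 4 |
| AE Worksheet, general question (8.5, Table 2) | yes | yes | yes | yes | 4 of 4 |
| Current abuse (8.4.7, Table 2) | yes | no | yes | yes | 3 of 4 |

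The CIDI does not fill the gap: Section 8.3.1 limits it to substance abuse subsections at baseline. A change score needs at least two measurements. The psychiatric domain has one, so no change score can be formed. Worsening can still be reported at all three follow-up visits through the Worksheet.

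**2. What the Worksheet yields.** It asks one general question and one follow-up question. Neither is described as specific to depression or anxiety, and no threshold is given for what counts as *marked*. The result is a reported event, not a symptom level.

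**3. What reaches the database.** The Study Clinician makes the final judgement of relatedness after talking with the staff member who reported the event (9.1.2). Section 6.3.2 describes an effort to blind only the research assistants who conduct assessments. Non-serious worsening judged unrelated stays on the AE Log. The database therefore holds distress already filtered by a case-by-case causal judgement, whereas in a randomised trial the difference between arms over all such events is itself the evidence on relatedness.

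**4. Opportunity to disclose.** Therapists report what they hear in sessions. From Section 6.1:

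- SSB: 5 sessions × 90 minutes = 450 minutes
- HE: 1 session × 60 minutes = 60 minutes
- Ratio: 450 / 60 = 7.5

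More distress could be recorded in SSB simply because there is 7.5 times as much scheduled contact in which to hear of it.

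**5. Time window.** SSB sessions run over three weeks (6.3). If *intervention phase* in Section 11.7 means the treatment period, reports from the 3- and 6-month visits fall outside the safety analysis. The protocol does not define the phrase otherwise.

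Point 4 would tend to raise the SSB count. Point 3 could act in either direction. Point 5 removes later events from both arms. The net direction cannot be known from the document.

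**The case against.** The strongest reply is that the protocol never relies on the ASI-Lite to detect this harm. The Worksheet asks directly about worsening at every follow-up visit, which is a within-person question about change. Section 9.1.3 trains research assistants and therapists to recognise signs of emotional distress. Participants are told from consent onward to raise such problems with staff. The DSMB conducts adverse-event analyses (9.1.4). Section 8.3.2 and Table 2 agree with each other, and Section 8.0 keeps visits short to protect follow-up. The protocol expects minimal risk. The abuse measure also serves as a candidate moderator, so its schedule is not purely a safety standard.

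Much of this stands. A reader might infer that an increase in distress cannot be measured in any of the roughly 480 women, or that it comes to light only if a woman volunteers it. The documents do not support either reading: the question is put to her at three post-intervention visits, and staff observation and session disclosure are further routes. Nor is trimming the ASI-Lite an internal contradiction.

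These routes detect and manage individual cases. They do not give a symptom level, and they do not collect information equally from both arms. The populations that Section 9.1.4 lists for the DSMB's adverse-event analyses are total, Node and CTP; no breakdown by arm is listed. The point is also not one for a later analysis plan, because no analysis can recover a score that the visit schedule does not collect.

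**Conclusion.** The point holds as a limit on comparison, not on detection. An increase in depression or anxiety can be reported after baseline, but its size cannot be estimated and the arms cannot be compared without bias. The psychiatric score exists at 1 of 4 time points; non-serious events judged unrelated never enter the database; scheduled time for session disclosure differs 7.5-fold; and the planned safety summary appears to stop at the end of the intervention phase.

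The conclusion rests on reading *intervention phase* as the treatment period and on taking Table 2 as the full list of scheduled measures. No rate of distress is assumed, and the document gives none. The primary efficacy analysis is unaffected. The matter is worth a small amendment because the harm is one that the protocol itself foresees.

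**What to change.** - **Section 8.3.2 and Table 2:** add the ASI-Lite psychiatric section to the drug and alcohol section at 3 and 6 months. Psychiatric scores would then exist at 3 of 4 time points, the same as current abuse. This assumes that its items cover depression and anxiety, which the protocol does not state. If they do not, use a brief symptom scale at baseline and both follow-ups instead.
- **Section 11.7:** report the difference between arms at follow-up, adjusted for the baseline score, with a 95% confidence interval that accounts for clustering by intervention group and site. If the score can be treated as continuous, model (2) in Section 11.6.2 already carries the baseline value and random effects for site, site-by-intervention and cluster, so no new method is needed. Include the result in the DSMB report.
- **Section 9.1.2 and Table 2:** reconcile the reference to an assessment of depression with the schedule, which contains none.

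The cost is a short amendment, a form change and a few more interview minutes at two visits where research staff already give another ASI-Lite section. The downside is slightly longer visits.
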